By identifying overall COVID-19 quality of life as well as specific associations or differences between COVID-19 and baseline local quality of life values, we hope to be able to provide evidence-based conclusions to medical practitioners trying to achieve the best quality of life for patients recovering from COVID-19.

Hypotheses

The null hypothesis is that recovered COVID-19 patients have no difference in quality of life compared to a normal control (baseline Hong Kong quality of life norms).

The alternative hypothesis is that there is a difference in quality of life measures between recovered COVID-19 patients and a normal control.

Plan of Investigation

Subjects

All adult patients aged ≥ 18 years who present to the infectious diseases specialist outpatient follow-up clinic at PWH will be screened for inclusion in this study. The inclusion criteria are age ≥ 18 years, laboratory-confirmed COVID-19 infection with SARS-CoV-2, and patients who agree to follow-up for up to six months following their first interview.

Exclusion criteria:

Patients aged below 18 years will be excluded.

Patients will be excluded if they meet ANY of the following criteria:

Patients or their next of kin are unable to communicate in Chinese or English,

Unwilling or unable to provide written informed consent,

or Patients who will not be available for telephone follow-up at the scheduled times.

We will record all patients who are not enrolled and the reasons for exclusion.

Sample size calculation

As of April 10, 2020, in the NTEC Hospital Authority cluster there have been 89 patients

admitted to PWH (of which 17 patients have already been discharged) and 117 admitted to United Christian Hospital with 42 discharged so far.²² Both PWH and United Christian Hospital's COVID-19 patients will follow-up at the PWH infectious diseases specialist outpatient follow-up clinic. Based on prior studies at PWH with SARS patients, approximately 80% agreed to participate in follow-up studies, so we will likely enroll approximately 200 COVID-19 patients.

Methods

This will be a prospective, observational, multicenter, cohort study. We plan to recruit 100 patients with laboratory confirmed COVID-19 disease who have been discharged from inpatient care or quarantine. Quality of life will be assessed using the SF-12v2(HK) and EQ-5D-5L survey instruments, and their return to work status will be measured up to six months from the date of discharge.

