The primary outcome measure will be the health summary scores from SF-12v2(HK) in COVID patients at six-months post-discharge from hospital.

Secondary outcomes

The secondary outcome measures will include the health status measures of the EQ-5D-5L and return to work status in COVID patients at six-months post discharge from hospital.

Other measures

The required clinical data for patient characteristics and data for investigating each patient’s relative illness severity will be collected at the earliest opportunity after subject enrollment. The final COVID-19 diagnosis and any other final diagnoses will be recorded from the patient’s existing clinical notes. The Hospital Authority’s computerized Clinical Management System (the

system used by all hospitals under Hospital Authority for storing and retrieving patients' data) will be reviewed to identify hospital admissions, emergency department reattendance, lengths of stay (intensive care, step-down units or general wards) and mortality.

Statistical analysis

General

Chi-square and Fisher's exact tests will be used for categorical data while t-tests will be used to compare means of continuous variables. A p value <0.05 will be considered statistically significant and all tests will be two-tailed.

Primary analysis

A univariate and multivariate analysis of the data set will be conducted at six months. SF-12v2 dimensions of survivors of COVID-19 will be compared with data from past survivors of SARS infection, sepsis or trauma. We will also compare this data to the general Hong Kong population summary score data. Data from the EQ-5D-5L survey instrument will be compared using the Chi-square or Fisher's exact tests.

Secondary analyses

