COVID-19 is still an incompletely understood disease. We will perform secondary analyses on the data to allow us to focus on specific groups and to adjust for variability. We will consider the severity of COVID-19 by examining each patient's clinical record, number of hospital days admitted, number of days spent in the intensive care unit, number and severity of organ(s) dysfunction, co-infections, pathogen(s) identified, pre-COVID-19 health status and pre-existing conditions. It is anticipated that there will be marked changes and differences in health status and functional outcome depending on patient age. Comparisons of quality of life between four time points (pre-sepsis, hospital stay, 3-months and 6-months after discharge) will be assessed using paired t-test or Wilcoxon (W) tests as appropriate.

Multivariate logistic regression analysis

All parameters will be entered into a multiple logistic regression model and used to evaluate associations and account for variation. Multiple logistic regression adjusts for variable interactions and will be used to identify predictors of quality of life in COVID-19 patients during follow-up.

References

1. World Health Organization. *Situation Report-78 HIGHLIGHTS.*; 2020. https://www.who.int/docs/default-source/coronavirus/situation-reports/20200407-sitrep-78-covid-19.pdf?sfvrsn=bc43e1b_2. Accessed April 10, 2020.
2. Centre for Health Protection of the Department of Health of the Hong Kong SAR. *Countries/Areas with Reported Cases of Coronavirus Disease-2019 (COVID-19).*; 2020. https://www.chp.gov.hk/files/pdf/statistics_of_the_cases_novel_coronavirus_infection_en.pdf. Accessed April 10, 2020.
5. Hui DS. Severe acute respiratory syndrome (SARS): Lessons learnt in Hong Kong. *J Thorac Dis.* 2013;5(SUPPL.2). doi:10.3978/j.issn.2072-1439.2013.06.18

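### The predictor model enters every parameter at once, with about 1 to 9 assumed events per parameter at 100 to 165 patients, so chance predictors and inflated odds ratios are likely

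*Combined protocol and SAP*

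**What the plan says.** The section Multivariate logistic regression analysis gives one rule for building the model: "All parameters will be entered into a multiple logistic regression model and used to evaluate associations and account for variation". Its purpose is that it "will be used to identify predictors of quality of life in COVID-19 patients during follow-up". The General paragraph of Statistical analysis sets two-tailed p<0.05 for all tests. There is no variable list, selection rule, penalisation, cap on coefficients or multiplicity control.

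Candidate parameters are spread over several sections:

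- Secondary analyses names severity from the clinical record, then "number of hospital days admitted, number of days spent in the intensive care unit, number and severity of organ(s) dysfunction, co-infections, pathogen(s) identified", then "pre-COVID-19 health status and pre-existing conditions". It also expects "marked changes and differences in health status and functional outcome depending on patient age".
- Other measures adds patient characteristics, other diagnoses, admissions, reattendance, and "lengths of stay (intensive care, step-down units or general wards) and mortality".
- First interview and Return to work status add the pre-COVID scores on both instruments and several employment items.

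On size, Methods says "We plan to recruit 100 patients", while Sample size calculation expects about 200. On the outcome, "The primary outcome measure will be the health summary scores from SF-12v2(HK) in COVID patients at six-months post-discharge from hospital". These scores are numeric, and no cut-point turns them into the binary outcome that a logistic model needs.

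**The concern.** A logistic model is limited by the smaller of its two outcome groups, not by the number of patients. Many coefficients fitted to few events push odds ratios away from 1. Judging each coefficient at 0.05 also makes it likely that at least one null variable looks like a predictor. The protocol hopes to give practitioners evidence-based conclusions about recovery, and a list of predictors that mixes noise with exaggerated effects would weaken that.

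Length of stay raises a second, conditional problem. Total hospital days is the sum of intensive care, step-down and ward days. If all four are entered, their separate effects cannot be estimated.

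**Working it through.** **Sample size.** The plan's own figure comes first. The inputs in Sample size calculation are 89 and 117 admitted patients and 80% participation: (89 + 117) × 0.80 = 206 × 0.80 = 164.8, or about 165. The printed figure of about 200 is not reproduced; it would need a pool of 200 / 0.80 = 250. The check uses 100 (Methods) and 165, with 200 for comparison. The plan gives no dropout rate, so none is subtracted, and the numbers at six months can only be lower.

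**Number of parameters.** Secondary analyses names eight items (organ dysfunction counted once). Age makes nine, at one coefficient each. Adding everything collected elsewhere gives about 20, before comorbidities, organisms and organ dysfunctions are coded into categories. Both counts are readings of the text, because the plan fixes no list.

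**Events per parameter** = N × event rate / parameters. The event rate is an assumption, shown from 20% to 50%; 50% is the most favourable value possible.

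| N | Parameters | 20% | 30% | 50% |
|---|---|---|---|---|
| 100 | 9 | 2.2 | 3.3 | 5.6 |
| 100 | 20 | 1.0 | 1.5 | 2.5 |
| 165 | 9 | 3.7 | 5.5 | 9.2 |
| 165 | 20 | 1.7 | 2.5 | 4.1 |
| 200 | 9 | 4.4 | 6.7 | 11.1 |
| 200 | 20 | 2.0 | 3.0 | 5.0 |

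Only one cell exceeds the usual rule of thumb of 10: 200 patients, 9 parameters, 50% events.

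**Chance predictors.** For k independent null tests at 0.05, the probability of at least one significant result is 1 − 0.95^k: 0.37 for k = 9 and 0.64 for k = 20. Simulated logistic fits (30% events, independent predictors, no true effects, N = 100 and 165) gave about 36 to 42% with 9 and 70 to 75% with 20. At N = 200 with 20 predictors the figure was 68%. The excess over the formula is the small-sample part; the rest is multiplicity.

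**Inflation.** In the same setting, a true odds ratio of 2.0 had a median estimate of about 2.1 to 2.2 with 9 parameters and 2.2 to 2.5 with 20.

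A second design used a true odds ratio of 1.5 per SD, mixed continuous and binary predictors, 9 to 20 parameters and 20 to 50% events. The median estimate was 1.53 to 1.79 over all converged fits, and 1.62 to 2.46 among those where that predictor was significant. Between 0 and 31% of fits failed to converge or showed separation, the highest at N = 100 with 20% events and 20 parameters.

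**Length of stay.** An intercept with intensive care, step-down, ward and total days has rank 4 for 5 columns, so the separate effects are not identified. An intercept with total and intensive care days has rank 3 for 3 columns, so both are estimable.

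**The case against.** The strongest reply is that this is a secondary analysis in an observational study, and that on the shorter reading (about 9 parameters) the harm is modest. Nine null tests give 37% by multiplicity alone, simulation adds little, and a true odds ratio of 2.0 is estimated at about 2.1 to 2.2. Ten events per parameter is only a rule of thumb. The event rate and the count of 20 are assumptions. All of this stands and limits the size of the point. It does not remove the point: the plan states a rule that leads to the longer list, and nothing in it stops the analyst there.

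A reader might infer more than the documents support:

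- **That the model cannot be estimated because the stay variables sum to each other.** Secondary analyses names only total and intensive care days, which are nested but not linearly dependent. Step-down and ward stays appear under Other measures and are not named as model terms. Even if all were entered, software would usually drop one column and fit the rest.
- **That identified pathogens duplicate co-infections because every patient has SARS-CoV-2.** Whether a co-infection is present and which organism causes it are different information.
- **That this model is the plan's sole source of predictors.** Primary analysis also plans univariate and multivariate analyses at six months, and Secondary analyses plans work by severity and patient group.
- **That overstated discrimination or loss of incomplete records can be quantified.** The plan proposes no discrimination measure and states no rule for missing values.

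**Conclusion.** The concern holds as a poor stated method, not as an impossible one. Entering all parameters and judging each at 0.05 is likely to name chance predictors and overstate real ones. The likelihood of at least one chance predictor, when nothing is predictive, runs from about 36 to 42% (9 parameters) to about 70 to 75% (20). These figures assume independent predictors and 30% events at 100 to 165 patients. Most of this is multiplicity, which more patients would not cure. Inflation of a true odds ratio of 2.0 is small with 9 parameters and clearer with 20 at N = 100.

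With the event rate varied from 20 to 50%, there are about 1 to 9 events per parameter at 100 to 165 patients. The true number of events is unknown until a cut-point is defined. The stay problem arises only if the total and all its components are entered.

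**What to change.** Replace the all-parameters rule with a short list fixed before analysis, containing one length-of-stay variable, and reconcile the planned sample size (100, about 200, or the derived 165).

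- **Preferred:** model the six-month physical and mental component summary scores as numeric outcomes by linear regression, with 10 to 15 patients per coefficient. At N = 100 that is 100 / 15 to 100 / 10, about 6 to 10 coefficients. It can carry, for example, age, sex, one acute-severity variable, one stay variable, a count of pre-existing conditions and the pre-COVID score of the same scale.
- **If a logistic model is kept:** define the binary outcome and allow about one coefficient per 10 events. At an assumed 30% that is 30 / 10 = 3 at N = 100 and 49.5 / 10, or 4 to 5, at N = 165. The six-term example would then be too long.
- **Other variables:** label them exploratory and, if they are fitted, use penalised estimation.

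A short list reduces the multiplicity but does not abolish it: six independent null terms still give 1 − 0.95^6 = 26%. The change needs only plan wording and a little analysis time, with no new data. The price is that fewer variables can be reported as independently tested predictors.

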Several instruments have been widely used in quality of life research, including the 36-Item Short Form Health Survey (SF-36), the 12-Item Short Form Health Survey (SF-12), the World Health Organization Quality of Life Instruments (WHOQOL-BREF), EuroQoL-5D (EQ-5D-5L) and the Short-Form Six-Dimension (SF-6D). Our team has experience using the SF-36, SF-12v2(HK) and the EQ-5D-5L survey instruments for monitoring quality of life in research subjects in Hong Kong. For example, we found that trauma patients in Hong Kong scored significantly worse on the SF-36 twelve months after injury.¹⁷ We also found the most dramatic improvements happened in the first one to six months post-injury,¹⁹ and that 45% of subjects had achieved an excellent outcome by four years post-injury.²⁰ The SF-12v2(HK) with four week recall is a modified version of the SF-36 to be shorter and quicker to use, while also already translated and validated in Hong Kong.²¹ We aim to combine our experience with conducting quantitative quality of life studies with the CUHK Department of M&T's expertise in coronavirus treatment and follow-up to explore the quality of life of COVID-19 patients in recovery.

The reported mortality rates for COVID-19 has so far been lower than SARS, although the higher absolute numbers of COVID-19 patients mean worldwide deaths are overall much higher. Trauma, sepsis and SARS survivors have all experienced significant long-term morbidity and decreased quality of life as a result of their injuries or infections. A previous study of patients infected with SARS-CoV-1 in 2003 at PWH showed that significant numbers of recovering patients had impaired long-term health status.¹² The question this study hopes to answer is to what degree do COVID-19 patients suffer a similar fate? Has the knowledge gained from the SARS experience led to improved quality of life outcomes compared to SARS survivors? Or do the similarities between the viruses that cause SARS and COVID-19 extend to a reduced quality of life after recovery as well?

Aims

This study aims to determine the quality of life of COVID-19 survivors up to six-months after discharge from hospital or quarantine. We also aim to compare the quality of life of COVID-19 survivors to baseline known Hong Kong quality of life norms.

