After written consent is obtained, the pre-COVID-19 and baseline information will be collected. Their COVID-19 information will be collected via face-to-face interview or telephone follow-up or by email. 1, 3 and 6-month data post-discharge will be collected via telephone follow-up interview with the patient or e-form completed by the patient.

Quality of life assessment tools

SF-12

The 12-Item Short Form Health Survey is an abbreviated version of the 36-Item Short Form Health Survey. It is a widely used, international, validated survey for investigating health-related quality of life in a variety of both acute and chronic conditions. The survey instrument has eight domains: physical functioning, physical role, bodily pain, general health, vitality, social functioning, emotional role, and mental health. Each domain is measured on a 0-100 scale. A higher score correlates with a higher quality of life. The survey generates a Mental Component Summary (MCS) and a Physical Component Summary (PCS). A Chinese version of the survey, the 12-item Chinese (Hong Kong) Short Form Health Survey (version 2) (SF-12v2 (HK)) has been previously validated and used in Hong Kong.²¹ We will be using the four week recall (standard) version of the SF012v2(HK).

EQ-5D-5L

The EQ-5D-5L is a brief health status measure that comprises of five domains: mobility, self-care, pain, usual activities, and psychological status. EQ-5D-5L has been validated in Hong

Kong, recently for use in patients with chronic obstructive pulmonary disease.²³

Return to work status

Patients' pre-COVID-19 infection work status will be compared to their post-infection status. The type of employment, salary and each patients' subjective work experiences before and after infection will be queried.

Definitions

COVID-19 = Coronavirus Disease 2019, the new disease pandemic caused by the SARS-CoV-2 virus.

CUHK = The Chinese University of Hong Kong

EQ-5D-5L = EuroQol Five Domain survey, one of the two main survey instruments we will use to quantitatively judge quality of life for enrolled study subjects.

NTEC = New Territories East Cluster, a grouping of healthcare facilities in northeast Hong Kong.

PWH = Prince of Wales Hospital, the largest acute care hospital in the Hong Kong Hospital Authority's New Territories East Cluster as well as the major teaching hospital for the Chinese University of Hong Kong's medical school.

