SARS = Severe Acute Respiratory Syndrome, the disease associated with the coronavirus epidemic of 2003 (not to be confused with SARS-CoV-2, which is the virus causing COVID-19 disease).

SARS-CoV-2 = Severe Acute Respiratory Syndrome Coronavirus 2, the virus identified as the causative organism of the COVID-19 disease.

SF-12 = The 12-Item Short Form Health Survey, one of the two main survey instruments we will use to quantitatively judge quality of life for enrolled study subjects. We will use the SF-12v2(HK) version of the SF-12, which has been specifically validated for use in Hong Kong.

Study design

Recruitment

All adult COVID-19 patients aged ≥ 18 years who present to the infectious diseases specialist outpatient follow-up clinic at PWH will be screened for inclusion in this study by research assistants involved in this study.

First interview

After consent, the pre-COVID-19 assessments of SF-12v2(HK) and EQ-5D-5L will be obtained

by face-to-face interview or by phone interview by a research assistant or by e-form completed by the patient. The interview process should take no longer than 10 minutes. The questionnaire may be completed by a proxy if the patient is unable to respond to the interviewer. Work status one month prior to COVID-19 diagnosis will be determined at this time as well.

Follow-up interviews

The SF-12v2(HK) and EQ-5D-5L will be obtained by telephone interview from the patient or e-form completed by the patient. The follow-up measures will be performed at 1, 3, and 6-months after date of recovery by a research assistant.

Studies have found differences between quality of life assessments completed by the patient or by proxy. In previous studies, it has been shown that when using EQ-5D-5L as an assessment tool, there is good agreement on the domain of self-care, but only a “fair” agreement on domains such as mobility, pain and anxiety were observed between the patients and caregiver rating.²⁴ However, if all proxy responses were excluded, quality of life for survivors of sepsis with communication problems would not be included, which would be a significant methodological and ethical problem. Thus, in this proposed study, the questionnaire may be completed by a proxy if the patient is unable to respond to the interviewer (e.g. patients with dementia or stroke). A subgroup analysis will be performed accordingly.

Data processing and analysis

Outcomes

Primary outcome

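### Predictors of quality of life over follow-up rest on one ordinary logistic regression, with no visit named and no model for repeated numeric scores

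*Combined protocol and SAP*

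**What the plan says.** Under Follow-up interviews, both instruments are repeated in every patient: "The follow-up measures will be performed at 1, 3, and 6-months after date of recovery by a research assistant". The Aims section covers the whole period: "quality of life of COVID-19 survivors up to six-months after discharge from hospital or quarantine".

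The section headed Multivariate logistic regression analysis gives the only model for predictors: "All parameters will be entered into a multiple logistic regression model and used to evaluate associations and account for variation". It adds that this model "will be used to identify predictors of quality of life in COVID-19 patients during follow-up". It names no visit, no clustering by patient and no definition of a good or poor outcome. The SF-12 description gives numeric scores: "Each domain is measured on a 0-100 scale". Two summary scores, physical (PCS) and mental (MCS), are derived from the survey.

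Two other statements bear on timing. The primary endpoint is fixed at one visit: "The primary outcome measure will be the health summary scores from SF-12v2(HK) in COVID patients at six-months post-discharge from hospital". The Primary analysis section says: "A univariate and multivariate analysis of the data set will be conducted at six months".

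The repeated nature of the data is addressed once, under Secondary analyses, by paired t-tests or Wilcoxon tests: "Comparisons of quality of life between four time points (pre-sepsis, hospital stay, 3-months and 6-months after discharge". That list leaves out the 1-month visit. No mixed model, generalised estimating equation (GEE) or robust standard error is named anywhere.

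**The concern.** Ordinary logistic regression assumes one independent binary record per patient. Here each patient supplies three correlated numeric records after discharge, and the model's stated scope is the follow-up period as a whole. Two analysts could follow this text, fit different models and both claim to have kept to the plan.

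The choice has consequences. Stacking the three visits as if they came from different people makes standard errors too small. The many candidate predictors (age, hospital and intensive care days, organ dysfunction, co-infection, prior conditions) would then yield too many spurious findings. Using six months alone avoids that, but the 1- and 3-month scores then contribute nothing to the predictor analysis. In neither case does the plan specify an estimate of whether severe or older patients recover more slowly or simply remain worse. That distinction matters to the clinicians whom the study hopes to inform.

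**Working it through.** **Inputs.** From the document: three follow-up assessments per patient, two-sided tests at 0.05, numeric scores. Assumed, because the document gives no value: equal correlation ρ between any two visits of 0.4, 0.6 or 0.7; a predictor that is constant within a patient; for the binary case, 30% poor outcomes. The plan gives no power, correlation or event rate for this model, so there is no figure of its own to reproduce. The error rates below depend little on whether 100 or 200 patients are recruited (both numbers appear in the plan).

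**1. Visits pooled, linear model.** The variance is understated by the design effect DE = 1 + (3 − 1)ρ. The true two-sided error is 2 × [1 − Φ(1.96/√DE)].

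| ρ | DE | 1.96/√DE | True error |
|---|---|---|---|
| 0.4 | 1.8 | 1.461 | 14.4% |
| 0.6 | 2.2 | 1.321 | 18.6% |
| 0.7 | 2.4 | 1.265 | 20.6% |

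**2. Visits pooled, logistic model.** Cutting a latent normal score so that 30% are poor turns latent correlations of 0.4, 0.6 and 0.7 into binary correlations of about 0.25, 0.39 and 0.48. The design effects are then about 1.50, 1.79 and 1.96, and the error rates 10.9%, 14.3% and 16.1%. Simulation with 100 patients (1,500 runs per setting) gave 10.5%, 14.3% and 15.7%. A second simulation (4,000 runs per setting, 100 and 200 patients) used binary correlations of about 0.28, 0.48 and 0.67. The pooled model gave 11.6–19.4%, the same data with errors clustered by patient 4.6–5.7%, and the six-month visit alone 4.2–5.0%.

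**3. Six months only, predictor with a common effect at all visits (linear model).** Relative to using all three visits, the standard error is multiplied by √[3/(1 + 2ρ)].

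- ρ = 0.4: √(3/1.8) = 1.29, so 29% larger
- ρ = 0.6: √(3/2.2) = 1.17, so 17% larger
- ρ = 0.7: √(3/2.4) = 1.12, so 12% larger

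The share of information lost is 1 − (1 + 2ρ)/3, which is 40%, 27% and 20%. It reaches 47% at ρ = 0.3.

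**4. Six months only, predictor whose effect may differ by visit.** With complete data and no other covariate, the joint model gives the same six-month effect and standard error as the single-visit model, so nothing is gained. Now add one covariate with a common effect, correlated 0.3 with severity (both standardised, covariance treated as known). The single-visit variance is proportional to 1/0.91 = 1.0989. The joint-model variance is proportional to 1 + (0.09/0.91)(1 + 2ρ)/3, which is 1.0593, 1.0725 and 1.0791. The ratios of standard errors are √(1.0989/1.0593) = 1.019, √(1.0989/1.0725) = 1.012 and √(1.0989/1.0791) = 1.009. The single-visit standard error is about 1–2% larger.

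**5. Course of recovery.** The paired tests use several time points but carry no predictors. The logistic model carries predictors but has no stated time structure. No planned analysis contains a predictor-by-visit term.

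**The case against.** The strongest reply is that the plan means a six-month model. The Primary analysis section places multivariate work at six months, and all primary and secondary endpoints are fixed there. With one record per patient, ordinary logistic regression keeps its error rate, as step 2 shows. The paired tests also show that the authors know the visits are dependent.

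Much of this stands, and it rules out two stronger readings. A reader might infer that the plan pools the visits and is therefore invalid. No text says so, and the 11–21% figures describe only what would follow if it were done. A reader might also infer that the only alternative to pooling is to throw away two thirds of the data. Two of the three follow-up records per patient would indeed go unused in a six-month model, but the information lost is about 20–47% for correlations of 0.7 down to 0.3. Separate models per visit or a per-patient summary are also compatible with the text, and the 3-month scores are used in the paired comparisons.

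Two further points are fair. The 12–29% precision figure does not carry over to the six-month effect of a predictor with a visit interaction (step 4). Adjusting for the pre-COVID-19 score would probably lower the residual correlation and so the inflation; at ρ = 0.3 the pooled linear error would be 12.1%.

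The reply does not close the gap. The six-month sentence stands under Primary analysis, whereas the logistic model has its own heading and its own, wider time frame. The course of recovery is not a formal hypothesis, but the Secondary analyses section anticipates marked changes by age and intends to take severity into account, and the planned methods cannot relate either to change over time.

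**Conclusion.** The point holds as a weakness in a secondary analysis that should be corrected. It does not affect the main comparison of six-month scores with Hong Kong norms. The plan applies a binary-outcome model without a cut-off to numeric scores, leaves the visits unspecified, and has no method that combines predictors with repeated visits.

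The size depends on the route taken. Pooling would raise the false-positive rate to about 11–16% (logistic) or 14–21% (linear). The six-month model is valid. It loses 12–29% in standard error for common-effect predictors and almost nothing for the six-month effect of a predictor that varies by visit, and it is silent on the course of recovery. All of these figures rest on assumed correlations of 0.4–0.7, the pooled logistic range also on a 30% poor-outcome rate, and the precision figures on complete data. The case for change therefore rests mainly on clear specification and the ability to study recovery over time, with precision a conditional benefit.

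**What to change.** For the predictor analysis, replace the logistic regression with one linear mixed model for PCS and one for MCS. Include visit (1, 3 and 6 months) as a factor, an unstructured within-patient covariance, the pre-COVID-19 score as a covariate, the pre-listed predictors and a severity-by-visit term. Report predictor effects at six months and the difference in course between 1 and 6 months. If age is also expected to alter the course, state an age-by-visit term in advance.

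If a binary outcome is preferred, define its cut-off before the data are seen and fit a GEE with robust errors clustered by patient.

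Merely naming six months as the sole visit would settle the question of validity, but it would leave the outcome undefined and the earlier scores outside the predictor analysis.

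The cost is a paragraph of SAP text and standard software, with no new data. The downside is slightly more modelling and a covariance structure that must be stated.
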